Atopic dermatitis (AD) is the most common chronic skin disease with clinical hallmarks of inflammatory lesions with an intense itch. In the World Health Organization (WHO) 2010 Global Burden of Disease survey, AD ranked first among common skin diseases with respect to disability-adjusted life-years and years lived with a disease (Murray et al. 2012; Vos et al. 2012). Currently, there is no cure for AD; thus, the aim of disease management is to improve symptoms and achieve long-term disease control with a multistep approach. There is a need for more efficacious therapies with a better safety profile than the standard of care for subjects with AD.

LY3375880 is a human immunoglobulin (Ig) G4-variant monoclonal antibody (mAb) that binds and neutralizes soluble human interleukin (IL)-33 cytokine. LY3375880 is being developed for the treatment of subjects with AD. This study will evaluate the safety and efficacy of LY3375880 in subjects with moderate-to-severe AD.

Objective(s)/Endpoints:

Objectives	Endpoints
Primary 
 To compare the efficacy of LY3375880 to placebo as measured by IGA at Week 16 in the treatment of subjects with moderate-to-severe AD. 	
 Proportion of subjects achieving IGA of 0 or 1 with a ≥ 2-point improvement at Week 16.
Secondary 
 To compare the efficacy of LY3375880 to placebo as measured by improvement in signs and symptoms at Week 16 and 52 in the treatment of subjects with moderate-to-severe AD. To characterize the PK of LY3375880 in subjects with moderate-to-severe AD 	
 Proportion of subjects achieving at Week 16: 
 EASI-50 EASI-75 EASI-90 SCORAD-75 SCORAD-90 IGA of 0 Mean change from baseline to Week 16 in: 
 EASI score SCORAD Proportion of subjects achieving IGA of 0 or 1 at Week 52

Abbreviations: AD = atopic dermatitis; EASI = Eczema Area and Severity Index; EASI-50/75/90 = 50%/75%/90% reduction in the EASI score; IGA = Investigator's Global Assessment; PK = pharmacokinetic(s); SCORAD = SCORing AD.

Summary of Study Design:

Study I9N-MC-FCAB (FCAB) is a Phase 2, multicenter, randomized, double-blind, placebo-controlled, parallel-group, outpatient study evaluating the efficacy and safety of LY3375880 subcutaneous (SC) 600 mg every 4 weeks (Q4W), 150 mg Q4W, and 50 mg Q4W as compared to placebo Q4W in adult subjects with moderate-to-severe AD. In addition, LY3375880 300mg Q4W will be evaluated during the maintenance period.

The study duration will be up to 65 weeks over 4 study periods:

- Period 1: Screening Period, lasting 8 to 35 days prior to Week 0 (baseline, Visit 2).
- Period 2: Induction Period, lasting from Week 0 (baseline, Visit 2) through Week 16 (Visit 8).
- Period 3: Maintenance Period, lasting from Week 16 (Visit 8) through Week 52 (Visit 17, inclusive).
- Period 4: Post-Treatment Follow-Up Period, lasting 8 weeks from Week 52 (after Visit 17) to Week 60 (Visit 801).

Treatment Arms and Duration:

Subjects will be randomized 1:1:1:1 at Week 0 to 1 of 4 treatment groups: placebo SC Q4W, LY3375880 SC 600 mg Q4W, LY3375880 150 mg Q4W, or LY3375880 50 mg Q4W. The study duration will be up to 65 weeks (Screening Period: Up to 5 weeks; Induction Period: 16 weeks; Maintenance Period: 36 weeks; Post-Treatment Follow-up Period: 8 weeks).

Number of Subjects:

Approximately 200 subjects will be randomized.

Statistical Analysis:

Efficacy will be conducted on the intent-to-treat population. Safety analyses will be conducted on the safety population.

Treatment comparisons of discrete efficacy variables between LY3375880 and placebo will be made using a logistic regression analysis with treatment, baseline disease severity (Investigator's Global Assessment [IGA] [3 versus 4]), and geographic region in the model. Treatment comparisons of the continuous efficacy variables will be made using a mixed-effects model of repeated measures (MMRM) analysis with treatment, baseline disease severity, geographic region, visit, and treatment-by-visit interaction as fixed categorical effects and, if a baseline score is available, baseline score and baseline score-by-visit interaction as fixed continuous effects. All tests of treatment effects will be conducted at a 2-sided alpha level of 0.05, with no control for multiple comparisons.

Fisher's exact test will be used for the adverse events (AEs), discontinuations, and other categorical safety data for between-treatment group comparisons. Continuous vital signs, body weight, and other continuous safety variables including laboratory variables will be analyzed by an analysis of covariance with treatment and baseline value in the model.

2. Schedule of Activities

Table FCAB.1. I9N-MC-FCAB Schedule of Activities

	Screening	Induction Period								Maintenance Period								Posttreatment Follow-Up
		Period 1				Period 2				Period 3								
Visit Number	1	2	3	4	5	6	7	8	9	10	11	12	13	14	15	16	17	801
Weeks from randomization		0	1	2	4	8	12	16	20	24	28	32	36	40	44	48	52 or ET	60
Days from randomization		0	7	14	28	56	84	112	140	168	196	224	252	280	308	336	364	420
Visit tolerance interval (days)	-8 to -35		±2	±2	±2	±4	±4	±4	±4	±4	±4	±4	±4	±4	±4	±4	±4	±5
Procedure																		
Inclusion and exclusion review	X	X																
Informed consent	X																	
Clinical assessments																		
Demographics	X																	
Medical history	X																	
Previous and current AD treatments	X																	
Weight		X																
Height		X																
Vital signs (BP and Pulse)	X	X	X	X	X	X	X	X	X	X	X	X	X	X	X	X	X	X
Complete physical examination	X																	
Symptom-directed physical examination ^a		X	X	X	X	X	X	X	X	X	X	X	X	X	X	X	X	X
Adverse events		X	X	X	X	X	X	X	X	X	X	X	X	X	X	X	X	X
Concomitant medication	X	X	X	X	X	X	X	X	X	X	X	X	X	X	X	X	X	X
ePRO (patient diary) dispensed	X	X		X	X	X	X	X	X	X	X	X	X	X	X	X	X	

	Screening	Induction Period								Maintenance Period								Posttreatment Follow-Up
		Period 1				Period 2				Period 3								
Visit Number	1	2	3	4	5	6	7	8	9	10	11	12	13	14	15	16	17	801
Weeks from randomization		0	1	2	4	8	12	16	20	24	28	32	36	40	44	48	52 or ET	60
Days from randomization		0	7	14	28	56	84	112	140	168	196	224	252	280	308	336	364	420
Visit tolerance interval (days)	-8 to -35		±2	±2	±2	±4	±4	±4	±4	±4	±4	±4	±4	±4	±4	±4	±4	±5
ePRO (patient diary) returned		X		X	X	X	X	X	X	X	X	X	X	X	X	X	X	X
Randomization		X						X ^b										
IWRS entry	X	X	X	X	X	X	X	X	X	X	X	X	X	X	X	X	X	X
IP SC injections		X			X	X	X	X	X	X	X	X	X	X	X	X	X	
Investigator Scales																		
IGA ^c	X	X		X	X	X	X	X	X	X	X	X	X	X	X	X	X	X
EASI ^c	X	X		X	X	X	X	X	X	X	X	X	X	X	X	X	X	X
SCORAD ^c	X	X		X	X	X	X	X	X	X	X	X	X	X	X	X	X	X
Health Outcome Measures and Other Questionnaires																		
POEM ^{c,d}	X	X		X	X	X	X	X	X	X	X	X	X	X	X	X	X	X
DLQI ^{c,d}	X	X		X	X	X	X	X	X	X	X	X	X	X	X	X	X	X
Itch NRS ^e	X	X		X	X	X	X	X	X	X	X	X	X	X	X	X	X	X
Skin Pain NRS ^e	X	X		X	X	X	X	X	X	X	X	X	X	X	X	X	X	X
C-SSRS “Baseline/Screening”	X																	
C-SSRS “Since Last Visit”		X	X	X	X	X	X	X	X	X	X	X	X	X	X	X	X	X
Self-Harm Supplement Form	X	X	X	X	X	X	X	X	X	X	X	X	X	X	X	X	X	X
Self-Harm Follow-up Form ^f	X	X	X	X	X	X	X	X	X	X	X	X	X	X	X	X	X	X

	Screening	Induction Period								Maintenance Period								Posttreatment Follow-Up
		Period 1				Period 2				Period 3								
Visit Number	1	2	3	4	5	6	7	8	9	10	11	12	13	14	15	16	17	801
Weeks from randomization		0	1	2	4	8	12	16	20	24	28	32	36	40	44	48	52 or ET	60
Days from randomization		0	7	14	28	56	84	112	140	168	196	224	252	280	308	336	364	420
Visit tolerance interval (days)	-8 to -35		±2	±2	±2	±4	±4	±4	±4	±4	±4	±4	±4	±4	±4	±4	±4	±5
Laboratory Assessment																		
12-lead ECG (single)	X																	
Chest x-ray ^g (posterior–anterior and lateral views)	X																	
TB test ^h	X																	
Read PPD if applicable (48–72 hours post-PPD) ⁱ	X																	
Skin punch biopsies ^j (lesional, nonlesional)		X		X		X		X										
Clinical chemistry	X	X		X	X	X	X	X	X	X	X	X	X	X	X	X	X	X
Hematology	X	X		X	X	X	X	X	X	X	X	X	X	X	X	X	X	X
Lipids (fasting) ^k	X						X										X	
Serum pregnancy ^l	X																	
FSH ^m	X																	
HIV, HCV, ⁿ HBV screening tests	X																	
HBV DNA ^o	X				X			X			X			X			X	X
Urinalysis	X	X						X				X						X
Urine pregnancy ^l		X		X	X	X	X	X	X	X	X	X	X	X	X	X	X	X
Pharmacogenetics sample	X																	
Serum IgE (total)		X		X			X										X	
Serum IgE (allergen)		X						X										

	Screening	Induction Period								Maintenance Period								Posttreatment Follow-Up
		Period 1				Period 2				Period 3								
Visit Number	1	2	3	4	5	6	7	8	9	10	11	12	13	14	15	16	17	801
Weeks from randomization		0	1	2	4	8	12	16	20	24	28	32	36	40	44	48	52 or ET	60
Days from randomization		0	7	14	28	56	84	112	140	168	196	224	252	280	308	336	364	420
Visit tolerance interval (days)	-8 to -35		±2	±2	±2	±4	±4	±4	±4	±4	±4	±4	±4	±4	±4	±4	±4	±5
specific) ^p																		
Exploratory long-term storage samples (serum, plasma EDTA)		X		X	X	X		X		X		X		X		X		
Exploratory long-term storage samples: RNA and DNA (epigenetic)		X			X			X									X	
LY3375880 PK Samples ^q		X	X	X	X	X		X		X		X		X			X	X
Immunogenicity samples ^q		X			X			X		X		X		X			X	X
Target engagement samples (Total IL-33)		X		X	X	X		X		X		X		X			X	
IL-19, TARC, Periostin		X		X	X	X		X		X		X		X		X	X	
Flow cytometry sample		X			X			X									X	

Abbreviations: AD = atopic dermatitis; BP = blood pressure; C-SSRS = Columbia-Suicide Severity Rating Scale (11 categories of suicidal ideation/suicidal behavior); DLQI = Dermatology Life Quality Index; DNA = deoxyribonucleic acid; EASI = Eczema Area and Severity Index; ECG = electrocardiogram; EDTA = ethylenediaminetetraacetic acid; ePRO = electronic subject-reported outcomes (device); ET = early termination; FSH = follicle-stimulating hormone; HBcAb = hepatitis B core antibody; HBsAb = hepatitis B surface antibody; HBsAg = hepatitis B surface antigen; HBV = hepatitis B virus; HCV = hepatitis C virus; HIV = human immunodeficiency virus; IGA = Investigator's Global Assessment; IgE = immunoglobulin E; IL = interleukin; IP = investigational product; IWRS = interactive web-response system; NRS = Numeric Rating Scale; PK = pharmacokinetic; POEM = Patient-Oriented Eczema Measure; PPD = purified protein derivative; RNA = ribonucleic acid; SC = subcutaneous; SCORAD = SCORing AD; TARC = thymus and activation-regulated chemokine; TB = tuberculosis.

- a The symptom-directed physical examination may be conducted at the investigator's discretion any time a subject presents with physical complaints.
- b Subjects will be re-randomized/reassigned at Week 16 as described in Section 5.
- c Will be collected as electronic Clinical Outcome Assessment (eCOA) data.
- d The following measures (POEM and DLQI) should be completed by the subject prior to any clinical assessments being performed on days when study visits occur.
- e Will be collected daily via an electronic subject diary.
- f The Self-Harm Follow-up Form is only required if triggered by the Self-Harm Supplement Form.
- g A posterior–anterior and lateral chest x-ray will be performed at screening unless one has been performed within the past 90 days, the x-ray and reports are available, and a repeat chest x-ray is not clinically indicated per investigator judgment.
- h TB test(s) including PPD, QuantiFERON®-TB Gold, and T SPOT®. See Exclusion Criterion [17] for description of TB testing. In countries where the QuantiFERON-TB Gold test or T-SPOT is available, either test may be used instead of the PPD TB test. The QuantiFERON-TB Gold test may be performed locally or centrally; the T-SPOT must be performed locally. (Note: Subjects who have a documented history of completing an appropriate TB treatment regimen for latent tuberculosis infection [LTBI] and with no risk of re-exposure since their treatments were completed are eligible to participate in the study if other criteria are met. These subjects should not undergo tuberculin skin test (TST) or interferon-gamma release assay (IGRA) testing unless advised to do so based on local guidelines, but must have a chest x-ray at screening.)
- i If PPD testing was chosen to test for TB, then the subject must return and PPD test read 48 to 72 hours after Visit 1 (post-PPD).
- j To be performed following investigator and subject disease assessments/scales.
- k Fasting lipid profile: Subjects should not eat or drink anything except water for 12 hours prior to sample collection. If a subject attends these visits in a nonfasting state, this will not be considered a protocol violation.
- l For all women of childbearing potential, a serum pregnancy test (central laboratory) will be performed at Visit 1. Urine pregnancy tests (local laboratory) will be performed at Visit 2 and subsequent visits according to the study schedule. If required per investigator judgment, local regulations, and/or institutional guidelines, additional pregnancy testing can occur during the study treatment period.
- m For female subjects to confirm post-menopausal status according to Inclusion Criterion [9].
- n For subjects who are positive for HCV antibody, a follow-up test for HCV RNA will be performed automatically. Subjects who are positive for HCV antibody and negative for HCV RNA may be enrolled.
- o Subjects who are HBsAg negative and positive for HBcAb (and/or HBsAb in Japan) will automatically have an HBV DNA performed at screening. Any patient positive for HBcAb and negative for HBV DNA may be enrolled and must undergo HBV DNA monitoring per the schedule (see Section 9.4.8).
- p Allergen-specific IgE testing could include, but is not limited to, *Dermatophagoides pteronyssinus*, *Dermatophagoides farinae*, *Alternaria alternata*.
- q PK and immunogenicity samples should be collected prior to dosing on days of dosing. Sites may be prompted to draw an unscheduled PK and immunogenicity sample based on EASI score entered. See Sections 9.4.9 and 9.5.

3. Introduction

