9.9. Medical Resource Utilization and Health Economics

Health Economics and Medical Resource Utilization parameters will not be evaluated in this study.

10. Statistical Considerations

Approximately 200 subjects will be randomized at a 1:1:1:1 ratio in the blinded induction dosing period to LY3375880 50 mg, 150 mg, 600 mg, and placebo (50 subjects per dosing regimen).

Assuming 36% and 8% of subjects achieve an IGA score of 0 or 1 (clear or almost clear skin) and ≥ 2 -point improvement from baseline at Week 16 for LY3375880 and placebo, respectively, pairwise comparisons to placebo have at least 90% power using a 2-sided Fisher's exact test at the 0.05 significance level, with no adjustment for multiple comparisons.

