10.2. Statistical Analyses

10.2.1. General Statistical Considerations

Statistical analysis of this study will be the responsibility of Lilly or its designee. A detailed SAP describing the statistical methodologies will be developed by Lilly or its designee.

Efficacy analyses will be conducted on the intent-to-treat (ITT) population. This set includes all randomized subjects, even if the subject does not take the assigned treatment, does not receive the correct treatment, or otherwise does not follow the protocol.

Safety analyses will be conducted on the safety population. This set includes all data from all randomized subjects receiving at least 1 dose of the IP according to the treatment to which the subjects were randomized.

When reported, descriptive statistics will include the number of subjects, mean, standard deviation, median, minimum, and maximum for continuous measures, and frequency counts and percentages for categorical measures.

Treatment comparisons of discrete efficacy variables between LY3375880 and placebo will be made using a logistic regression analysis with treatment, baseline disease severity (IGA 3 versus 4), geographic region, and, if applicable, baseline scores (such as baseline EASI score for a comparison of EASI-75) in the model. The percentages, difference in percentages, and 95% confidence interval (CI) of the difference in percentages will be reported. Treatment-by-region interaction will be added to the logistic regression model of the primary and key secondary

variables as a sensitivity analysis. If this interaction is significant at a 2-sided 0.1 level, further inspection will be used to assess whether the interaction is quantitative (i.e., the treatment effect is consistent in direction but not size of effect) or qualitative (the treatment is beneficial for some but not all regions).

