### **5.2.3. Analysis Methods**

The main analysis of categorical efficacy variables and health outcomes variables will use a logistic regression analysis with region, baseline disease severity (IGA) and treatment group in the model. The p-value and 100(1-alpha)% CI for the odds ratio from the logistic regression model are used for primary statistical inference. The difference in percentages and 100(1-alpha)% CI of the difference in percentages using the Newcombe-Wilson without continuity

correction will be reported. The p-value from the Fisher's exact test will also be produced as a secondary analysis.

The main analysis for all continuous efficacy and health outcomes variables will use mixed model repeated measures (MMRM) analysis. The MMRM model will use a restricted maximum likelihood (REML) estimation. The model will include treatment, region, baseline disease severity, visit, and treatment-by-visit-interaction as fixed categorical effects and baseline and baseline-by-visit-interaction as fixed continuous effects. An unstructured (co)variance structure will be used to model the between- and within-patient errors. If this analysis fails to converge, the heterogeneous autoregressive [ARH(1)], followed by the heterogeneous compound symmetry (CSH), followed by the heterogeneous Toeplitz (TOEPH) will be used. The Kenward-Roger method will be used to estimate the degrees of freedom. Type III tests for the least-squares means (LSM) will be used for the statistical comparison. The LSM difference, standard error, p-value and 100(1-alpha)% CI will also be reported.

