### **5.11.1. Primary Outcome and Methodology**

The validated Investigator's Global Assessment for AD (IGA) uses the clinical characteristics of erythema, papulation/induration, oozing/crusting and lichenification to produce a single-item score ranging from 0 to 4. The primary analysis of the study is to test the hypotheses that LY3375880 600-mg, LY3375880 150-mg, or LY3375880 50-mg is superior to placebo when evaluating the proportion of patients achieving IGA of 0 or 1 with a  $\geq 2$ -point improvement from baseline at Week 16 using the ITT population. A logistic regression analysis as described in Section 5.2.3 will be used for the comparisons. The odds ratio, the corresponding 95% CIs and p-value, as well as the treatment differences and the corresponding 95% CIs, will be reported. Missing data will be imputed using the NRI method described in Section 5.4.1.

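### The primary Week 16 IGA model adjusts for baseline severity only as IGA 3 versus 4; adding the baseline EASI already collected would be a low-cost improvement, with a gain that depends on its unknown prognostic strength

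*Protocol*

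**What the plan says.** The Protocol synopsis (Statistical Analysis) describes the logistic model for discrete efficacy variables as treatment plus baseline severity and region: the Investigator's "Global Assessment [IGA] [3 versus 4]), and geographic region in the model".

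Protocol 10.2.1 repeats this and adds, "if applicable, baseline scores (such as baseline EASI score for a comparison of EASI-75) in the model". The example is a measure's own baseline score. For the IGA endpoint that score is IGA itself. Entry requires IGA of at least 3 on a 0 to 4 scale (Protocol 6.1, 9.1.1.1), so baseline IGA takes two values and is already the severity factor. The clause therefore adds nothing to the primary model.

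SAP 5.2.3 says the main categorical analysis "will use a logistic regression analysis with region, baseline disease severity (IGA) and treatment group in the model". SAP 5.11.1 applies this to the primary endpoint: "A logistic regression analysis as described in Section 5.2.3 will be used for the comparisons". SAP 5.3 adjusts for the two stratification factors and adds a baseline value only for MMRM.

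EASI is scheduled at Visit 2 (Protocol Section 2) and must be at least 16 there (Protocol 6.1, criterion 4). Its maximum is 72 (Protocol 9.1.2.1).

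**The concern.** Two IGA levels are a coarse measure of starting severity. Subjects who share an IGA level can differ in EASI, and those who start higher may have further to go to reach clear or almost clear skin. If so, leaving EASI out costs some power for each dose comparison.

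It also leaves chance differences in EASI between arms uncorrected within IGA levels. With about 50 subjects per arm and a trial meant to inform dose selection (Protocol 5.4), such a difference could make one dose look better or worse than it is and invite argument after the results are known.

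**Working it through.** **1. The plan's own figure.** Protocol Section 10 gives 50 per arm, "randomized at a 1:1:1:1 ratio in the blinded induction dosing period". The rates are stated as follows: "Assuming 36% and 8% of subjects achieve an IGA score of 0 or 1 (clear or almost clear skin"). The claim is that "pairwise comparisons to placebo have at least 90% power", by a two-sided Fisher's "exact test at the 0.05 significance level, with no adjustment for multiple comparisons".

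Power = sum over a, b of Bin(a; 50, 0.36) x Bin(b; 50, 0.08) x 1[Fisher p <= 0.05] = **91.4%** (49 per arm: 90.7%; 48 per arm: 89.9%). The stated figure holds and relies on no covariate.

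**2. Effect of adding EASI on power.** Simulated model, four arms of 50:

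logit P(response) = a(arm) + g x [IGA 4] + b x z

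Here z is EASI standardised within IGA level, and a(arm) is solved to give the required overall response rate. These inputs are assumed because the documents do not give them: half the subjects at IGA 4; g = -0.7 (run A: ln 0.5 = -0.69); 20% Japan with no effect; z normal; and b itself. Each simulated trial is analysed twice, with treatment + IGA + region and with the same model plus z. The Wald test compares dose with placebo.

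Power without -> with EASI (run A: 4000 trials per scenario; run B: 3000):

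| b per SD | Run | 36% v 8% | 28% v 8% (28% assumed) |
|---|---|---|---|
| 0 | A | 93.3 -> 93.3 | 73.3 -> 73.6 |
| -0.22 (OR 0.8) | A | 92.4 -> 92.6 | 73.0 -> 73.5 |
| -0.40 (OR 0.67) | A | 92.4 -> 93.1 | 74.0 -> 75.2 |
| -0.4 | B | 92.3 -> 92.8 | 74 -> 75 |
| -0.69 (OR 0.5) | A | 93.0 -> 94.1 | 74.2 -> 76.8 |
| -0.7 | B | 93.1 -> 94.1 | 73 -> 76 |
| -0.92 (OR 0.4) | A | 92.4 -> 94.4 | 73.2 -> 78.1 |
| -1.0 | B | 93.1 -> 95.7 | 73 -> 79 |

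The gain is 0 to 2.6 points at the design rates (95.7 - 93.1 = 2.6) and about 0 to 6 points at 28% (79 - 73 = 6). At an assumed 20% (run B), power moves 37 -> 37, 36 -> 39 and 36 -> 40 for b = -0.4, -0.7 and -1.0. In run A the Monte Carlo standard error of each power is sqrt(0.93 x 0.07/4000) = 0.4 points at 36% and sqrt(0.73 x 0.27/4000) = 0.7 points at 28%. Both models are fitted to the same trials.

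**3. Null level.** With every arm at 15%, rejection is 3.7% to 4.5% without EASI and 4.0% to 4.2% with it. With the tested arm and placebo both at 8%, the Wald test rejects in 1.4% to 1.8% without and 1.4% to 2.2% with. The likelihood-ratio test rejects in about 7% either way. The choice of test matters at 8%; the EASI term barely does.

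**4. Chance imbalance.** The difference between two arms in mean z has SD sqrt(2/50) = 0.2. So P(|difference| > 0.3) = P(|Z| > 1.5), about 13% for one comparison with placebo. By simulation, at least one of the three exceeds 0.3 SD in about 30% of trials. P(active arm worse by more than 0.2 SD) = P(Z > 1), about 16%.

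Power for 28% v 8% in trials with an imbalance of more than 0.2 SD, without -> with EASI (6000 trials per scenario):

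| b per SD | Active arm worse | Active arm milder |
|---|---|---|
| -0.4 | 70 -> 79 | 78 -> 71 |
| -0.7 | 62 -> 78 | 83 -> 74 |
| -1.0 | 57 -> 79 | 88 -> 77 |

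Without the covariate, power swings with the imbalance in both directions. With it, power stays in the 70s. Each subset holds about 0.16 x 6000 = 960 trials, so these figures carry an error of about 1.5 points.

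**The case against.** The strongest case is that this is a preference. The model adjusts for exactly the two stratification factors, the test is valid, and the planned power is met without any covariate. All of that stands.

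The prognostic strength of EASI within an IGA level is also unknown. The two scales overlap (both score erythema, induration/papulation and lichenification), and the scale limits of 16 and 72 say nothing about the actual spread. At weak effects the gain is nil; one further run at b = -0.2 gave 93.5 -> 93.4, which is noise. The simulated EASI is normal, whereas entry truncates it at 16. These points limit the size of the claim.

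A reader might infer that the primary analysis gives up free power. The documents do not support that. Any loss depends on a figure they do not contain, and the term is not quite free, with only 0.08 x 50 = 4 placebo responders expected. Nor do they show that the lower doses are underpowered: the only active rate planned is 36%, and 28% and 20% are assumptions. Protocol 5.5 says the doses should cover a minimal-to-maximal effect range, which makes a lower rate plausible but does not state one.

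The plan does not ignore baseline EASI. SAP 5.8.2 summarises it, SAP 5.14 splits the primary endpoint at its median, and the MMRM for EASI adjusts for it. These steps would reveal an imbalance, but none of them adjusts the primary comparison.

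**Conclusion.** The point holds as an inexpensive improvement to a valid analysis. The primary model leaves out a continuous severity measure that every eligible subject has. No stated figure is wrong.

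Over the assumed prognostic range, the average gain is small at the design rates and moderate if a dose falls short of them. The stronger reason is protection from chance imbalance, which matters only if EASI is prognostic within IGA levels. If it is not, essentially nothing is lost. The benefit reaches the odds ratio and its p-value, on which SAP 5.2.3 bases primary inference. The Newcombe-Wilson difference in percentages is unadjusted and would not change.

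**What to change.** Before any unblinding, including the interim look at 40% to 60% completion (SAP 5.16), add baseline (Visit 2) EASI as a continuous covariate to the logistic model for the primary endpoint. Amend Protocol 10.2.1 and 10.2.3.1 and SAP 5.2.3, 5.3 and 5.11.1, and align the synopsis. Keep IGA 3 versus 4 and region in the model.

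Apply the term to Week 16 IGA 0 only if responder counts support it. At an assumed placebo rate of 1% to 3%, a placebo arm of 50 has no responder with probability 0.99^50 = 61% to 0.97^50 = 22%, and an EASI term does not help with that.

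If the sponsor prefers to keep the present primary model, prespecify the EASI-adjusted model as a sensitivity analysis.

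The cost is wording and one model term, with no new data and essentially no subjects lost. The downsides are that the odds ratio becomes conditional on one more covariate, and that one more parameter is fitted with few placebo responders.
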